2. OBJECTIVES

2.1. Primary objective

- To assess the risk of spontaneous abortion during weeks 1 to 23 of gestation (UK definition) in women aged 15 to 25 years with the first day of LMP between 30 days before and 45 days after any dose of *Cervarix*.

Refer to 5.1.1 for the definition of the primary endpoint.

2.2. Secondary objective

- To assess the risk of spontaneous abortion during weeks 1 to 23 of gestation (UK definition) in women aged 15 to 25 years with the first day of LMP between 30 days before and 90 days after any dose of *Cervarix*.

- To assess the risk of spontaneous abortion during weeks 1 to 19 of gestation (US definition) in women aged 15 to 25 years with the first day of LMP between 30 days before and 45 days after any dose of *Cervarix*.
- To assess the risk of spontaneous abortion during weeks 1 to 19 of gestation (US definition) in women aged 15 to 25 years with the first day of LMP between 30 days before and 90 days after any dose of *Cervarix*.
- To assess the risk of other pregnancy outcomes in women aged 15 to 25 years with the first day of LMP between 30 days before and 45 days after any dose of *Cervarix*.
- To assess the risk of other pregnancy outcomes in women aged 15 to 25 years with the first day of LMP between 30 days before and 90 days after any dose of *Cervarix*.

Refer to 5.1.2 for the definition of the secondary endpoints.

3. STUDY DESIGN

- This is an observational cohort study using the CPRD *GOLD* data source in the UK.
- Two cohorts will be defined based on the first day of gestation and exposure to *Cervarix* as recorded in the CPRD *GOLD* data source.
- This is a Targeted Safety Study (TSS) and a Post Authorisation Safety Study (PASS).
- Type of study: Self-contained.
- Epoch 001 (Table 1): Data collection.

Table 1 Study groups and epochs foreseen in the study

Study Groups	Number of subjects	Age (Min/Max)	Epochs
			Epoch 001
exposed cohort	Approximately 240 (-30 to +45 day window) and 380 (-30 to +90 day window)	15-25 years	x
non-exposed cohort	Approximately 660	15-25 years	x

(Amended 14 March 2013)

3.1. HPV vaccine coverage and pregnancy rate in the UK teenagers

In the UK public HPV immunization program (12-13 year olds), HPV vaccination coverage in the UK for 2009 was 88.1%, 86.0% and 80.1% for the first, second and third dose respectively. The coverage in the catch-up program for women (15-18 years old) was 62.2%, 54.2% and 31.8% for the first, second and third dose, respectively [Sheridan, 2009]. ***HPV vaccination coverage in the UK for 2010/11 was 89.0%, 87.6% and 83.8% for the first, second and third dose respectively [Health Protection Agency, 2012].***

The teenage pregnancy rate in the UK is reported to be around 40,000 teenage pregnancies each year [ONS, 2009; ONS, 2010]. For girls aged 15-17 years, the

provisional number of conceptions in England was 35,966 in 2009, reflecting a conception rate of 38.2 per 1000 person years. The pregnancy rate in females 15-17 years in the US is estimated at 42 per 1000 in 2004 [Ventura, 2008].

(Amended 14 March 2013)

3.2. Feasibility analysis and limitations of the study design

A feasibility analysis of HPV vaccination records and pregnancy outcomes data in CPRD *GOLD* database was performed by GSK.

Immunization with HPV vaccine is coded in the CPRD *GOLD* with the following codes: 93489, 93621, and 95554 for the 1st, 2nd and 3rd dose, respectively.

Exploration of the CPRD *GOLD* database identified 148,731 vaccinated subjects (Table 2) and 83,686 aged between 15 and 25 years (Table 3).

Table 2 Counts of HPV vaccination per year in the CPRD *GOLD*

Year of vaccination	N
2007	247
2008	29,301
2009	87,233
2010	29,364
2011	2,586

Created by GSK Biologicals, 2012

Data extracted from CPRD *GOLD* version ffcprd_smart_2012Q3

Table 3 Number of HPV vaccinations per age range in the CPRD *GOLD*, 2007-2011

Age Range	N subjects HPV
9-14	64,667
15-19	82,382
20-25	1,304

Created by GSK Biologicals, 2012

Data extracted from CPRD *GOLD* version ffcprd_smart_2012Q3

However, data on HPV vaccination status is not captured for all vaccinees in CPRD *GOLD* (lack of sensitivity) and absence of a vaccination record does not imply absence of vaccination. For instance, 70.7% of the 01SEP1996 – 31AUG1997 birth cohort was reported as HPV vaccinated in CPRD *GOLD* vs. 85.9% reported by the UK Health Protection Agency (HPA). Corresponding numbers for the 01SEP1994 – 31AUG1995 birth cohort are 70.6% vs. 81.9% (Table 4).

Table 4 HPV vaccination coverage in CPRD GOLD and HPA data

Birth Cohort	CPRD GOLD **			UK*
	N vaccinated	N total	%	%
01SEP1996 and 31AUG1997	16,028	22,685	70.7%	85.9%
01SEP1994 and 31AUG1995	16,343	23,143	70.6%	81.9%

Created by GSK Biologicals, 2012

*From Health Protection Agency Department of Health [Health Protection Agency, 2012]

** Data extracted from CPRD **GOLD** version ffcprd_smart_2012Q3

To overcome this limitation related to incomplete vaccination records, the non-exposed cohort will include *Cervarix* vaccinated women who have had the first day of gestation between 120 days and approximately 18 months after the last *Cervarix* dose. That would increase the specificity in the control group since it would be very unlikely for women to be vaccinated again after completing the three HPV doses. This is also the design agreed with the FDA for the study in the US (EPI-HPV-020).

Contrary to the lack of sensitivity in the overall population, a lack of specificity in the vaccine records is very unlikely, because vaccination is an important event.

Subjects in the non-exposed cohort are believed to be comparable to those in the exposed cohort as both have received *Cervarix* and a possible risk linked to vaccination could be reasonably excluded because of the delay between vaccination and first day of gestation. Hence, the non-exposed cohort may be slightly older than the exposed cohort. Although it is expected that the difference will be approximately one year, the analysis of primary endpoint will be adjusted for the age at first day of LMP.

The number of subjects in CPRD **GOLD** with at least one pregnancy in the study period from January 1st 2007 to June 30th 2011 by age range, among HPV vaccinated and non-vaccinated women, are provided in Table 5.

Table 5 Pregnancies in the CPRD GOLD within the study period (≥ Jan 1st, 2007)

Age Range	N pregnant and HPV vaccinated women	N total pregnant women
[11 - 15]	2,155	5,066
[16 - 20]	8,232	60,438
[21 - 25]	181	84,932
[26 - 30]	36	103,803
[31 - 35]	14	87,153
[36 - 40]	6	46,224
[41 - 45]	5	13,861
[46 - 50]	6	4,174

Based on CPRD **GOLD** version ffcprd_smart_2012Q3.

Procedure: This analysis is a feasibility using a preliminary list of pregnancy identifiers, no use of free text. We selected the subject identifiers and the pregnancy identifier event date from the clinical data in CPRD **GOLD** and matched on immunization codes from HPV (93489, 93621, 95554), restricting the event date from January 1st 2007 to June 30th 2011. For determination of the total pregnancy number, the same procedure was used, except for the matching on

immunization codes. These data are then matched to each female subject's year of birth to select the age at onset of the pregnancy identifiers. The number of subjects vaccinated and the total number of pregnant subjects are tabulated by 5 year age-classes from 11 to 50. If there are multiple pregnancy indicators per subject then the one with the earliest date is used.

Based on the recent CPRD **GOLD** release (2012Q3), 2440 subjects out of 78,111 subjects (3.1%) 15-25 years of age and exposed to *Cervarix* were identified with a simultaneous *Cervarix* vaccination and a LMP date between September 1st 2008 and June 30th 2011. Among these potential eligible subjects (not taking into account all inclusion/exclusion criteria as defined below in this protocol), 243 were identified as being exposed to *Cervarix* vaccine (first day of LMP between 30 days before and 45 days after any dose), 379 (first day of LMP between 30 days before and 90 days after any dose) and 667 as non-exposed (first day of LMP between 120 days and 18 months after the last dose of *Cervarix* vaccine).

The estimate for spontaneous abortions in the CPRD **GOLD** of 11.6% is in line with earlier literature reports in US and UK [e.g. 13.8%, Saraiya, 1999; 7.0%, Seamark, 2001; 14.0%, Ventura, 2008; 11.5% and 10.2%, Wacholder, 2010; 14.9%, Devine, 2010].

Based on the numbers obtained above, the proposed study could be performed using CPRD **GOLD** data source. The risk of spontaneous abortions in the exposed cohort will be compared to that in the non-exposed cohort.

(Amended 14 March 2013)

[figure not shown]
4. STUDY POPULATION

4.1. Study cohorts

Two cohorts of pregnant women will be defined based on exposure to *Cervarix* as recorded in the CPRD **GOLD** (Figure 1) **(Amended 14 March 2013)**:

- The **exposed cohort** will include women with the first day of LMP: between 30 days before and 45 days after any *Cervarix* dose, as requested by the FDA, and between 30 days before and 90 days after any *Cervarix* dose, as defined in the study EPI-HPV-020 and as used for the pooled analysis by Wacholder [Wacholder, 2010].
- The **non-exposed cohort** will include women with the first day of LMP between 120 days and 18 months after their last *Cervarix* dose (and no further *Cervarix* dose before the outcome).

Figure 1 Definition of exposure and non-exposure

Note: Last dose can be first or second dose if no subsequent dose was administered.

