4.2.2.2. Inclusion criteria for non-exposed cohort

All subjects must satisfy all of the following criteria at entry into the non-exposed cohort:

- Full date (day/month/year) of first day of LMP available in the database or calculated from EDD (day/month/year)
- Female, aged between, and including, 15 and 25 years of age at LMP
- Recorded in the CPRD **GOLD** since at least 12 months at LMP
- First day of LMP available in the database or calculated from EDD (day/month/year) between September 1st 2008 and June 30th 2011
- At least one dose of *Cervarix* received between September 1st 2008 and June 30th 2011
- Full date (day/month/year) of *Cervarix* vaccination(s) available
- First day of LMP available in the database or calculated from EDD between 120 days and 18 months after the last dose of *Cervarix*
- Subject defined as acceptable in CPRD **GOLD**

(Amended 14 March 2013)

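### Section 4.1 restricts the non-exposed cohort by doses given after LMP, which can inflate comparator risk, probably slightly; 'last dose' needs one fixed as-of date

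*Combined protocol and SAP*

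**What the plan says.** Three places define the non-exposed cohort.

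- Section 4.1 requires LMP between 120 days and 18 months after the last dose and adds "and no further *Cervarix* dose before the outcome".
- The note to Figure 1, directly below, reads "Note: Last dose can be first or second dose if no subsequent dose was administered". It admits women with one or two doses and sets no time limit on the later dose.
- Section 4.2.2.2, the inclusion list, asks only for LMP "between 120 days and 18 months after the last dose of *Cervarix", without the Section 4.1 condition. Its lead-in is "All subjects must satisfy all of the following criteria at entry into the non-exposed cohort".

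The exposed window runs from LMP 30 days before to LMP 90 days after a dose (Sections 4.1 and 4.2.2.1). The exposed cohort has no matching condition on later doses. Section 5.5.1 counts women who fit neither cohort as non-eligible. Section 3.2 argues that further doses are rare because "it would be very unlikely for women to be vaccinated again after completing the three HPV doses", which covers only women with a complete course. None of the sensitivity analyses in Sections 5.5.3.1 and 5.6.3.1 deals with doses after LMP.

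**The concern.** Time zero for the Cox model is the first day of gestation. Whether a woman has a further dose before her outcome is known only later, and it depends on how long the pregnancy lasts. A woman whose first post-LMP dose comes more than 30 days after LMP, while she is still pregnant, is outside the exposed window and is removed from the comparator by Section 4.1. Had she miscarried the week before that dose, she would have been kept, with her event. The rule thus removes event-free follow-up and keeps losses. In a safety study this is the unwelcome direction: comparator risk rises and a harmful HR moves toward 1.

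The undated wording adds a second uncertainty. If the last dose meant the last ever recorded (the database runs to June 2012), a woman who miscarried and then resumed her course could leave the comparator, which would push the HR up.

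**Working it through.** **Inputs.** Spontaneous abortion risk p = 11.5% (Section 5.4); 243 exposed in the primary window and 667 non-exposed (Section 3.2). The plan gives no count of women dosed after LMP, so every share below is an assumption.

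**Yardstick from the plan.** Freedman's log-rank formula with φ = 243/667 = 0.364 and d = 667 × 0.115 + 243 × (1 − 0.885²) = 76.7 + 52.7 = 129.4 events gives z = √(0.364 × 129.4)/(1 + 2 × 0.364) − 1.96 ≈ 2.01. Power is 97.8% and the HR detectable with 80% power is 1.68, against 98% and 1.69 in Section 5.4. This match does not remove the listed 20% dropout; removing it in full gives 94.4% and 1.77.

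**Section 4.1 rule.** Drop a share x of continuing comparator pregnancies and keep all losses. With no true effect, the ratio of exposed to comparator risk becomes p + (1 − p)(1 − x) = 1 − 0.885x.

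- x = 1%: 0.885 × 667 × 0.01 = 5.9 women dropped; comparator risk 76.7/661.1 = 11.6%; factor 0.99.
- x = 5%: 29.5 women dropped; comparator risk 76.7/637.5 = 12.0%; factor 0.956. As a ratio of cumulative hazards, ln(0.885)/ln(1 − 0.1203) = 0.953.

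A simulation also let some losses occur after the dose (dose uniform on days 31–161; time of loss triangular with minimum 35, mode 63 and maximum 140 days). If 5%, 10% or 20% of women would get such a dose while still pregnant, a true HR of 1.0 is estimated as 0.97, 0.94 or 0.87.

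**Literal last-dose-ever reading.** Let a later dose remove a share f of continuing and g of miscarrying women. Comparator risk = p(1 − g)/[p(1 − g) + (1 − p)(1 − f)].

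- f = 5%, g = 10%: 0.1035/(0.1035 + 0.8408) = 11.0%, HR 1.05.
- f = 10%, g = 20%: 10.4%, HR 1.12.
- f = 20%, g = 40%: 8.9%, HR 1.31.
- f = g: no bias.

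**Who can be affected.** The only schedule in the documents is 0, 1 and 6 months, in the title of the cited pre-licensure trial (Section 9). It puts dose 3 about 150 days after dose 2. With LMP at least 120 days after dose 2, an on-time dose 3 comes no later than about 150 − 120 = 30 days after LMP, which makes the woman exposed. Only late doses trigger the Section 4.1 exclusion.

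**Against sampling error.** With 243 × 0.115 = 27.9 and 76.7 events, SE(log HR) = √(1/27.9 + 1/76.7) = 0.22, so the 95% CI spans a factor of about exp(1.96 × 0.22) = 1.54 each way. A factor of 0.956 is 0.045/0.22 ≈ 0.2 SE. Power is not the issue: on the no-loss basis it is still 97.3% with 606 comparators and 96.6% with 544.

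**The case against.** The cohort is defined mainly by a dose before LMP. A reader might infer that doses after LMP define it, but they are only an added restriction, and it matters only for women who receive another dose.

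A reader might also infer that the plan contains two conflicting rules. The documents do not establish that. The note can be read as a gloss on the condition just above it, saying only that the last dose need not be the third. Section 4.2.2.2 applies its criteria at entry, when a dose after a miscarriage does not yet exist. The upward bias therefore rests on a literal reading that this lead-in argues against. Cohort identification is also delegated to algorithms in Appendix A, whose content is not in the text available here, so the operational rule may be settled there.

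The coverage figures ("62.2%, 54.2% and 31.8% for the first, second and third dose, respectively") might suggest that many women are at risk, since (54.2 − 31.8)/54.2 = 41% of two-dose women had no third dose. That is a population gap in 2009 data, before the catch-up programme ended, and can include women not yet due. It does not measure late doses during pregnancy. Section 1.2 says the vaccine is not recommended in pregnancy, which makes such doses less likely still.

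All of this stands, and it limits the size of the problem. It does not remove the mechanism: even with the note read as a gloss, Section 4.1 selects on what happens between LMP and outcome. That condition cannot be checked at entry, and the inclusion list omits it.

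**Conclusion.** The point holds as a matter of definition with a probably small effect. Followed as written, Section 4.1 over-retains losses in the comparator and can pull the HR toward or below 1. The factor is about 0.99 to 0.96 if 1% to 5% of continuing non-exposed pregnancies are dropped; these shares are assumed. The larger shifts, 0.87 in the simulation or 1.31 under the literal reading, need shares for which the documents give no support. It would go too far to say that the comparator is biased or that harm is hidden: the number of women affected is unknown, and the 1% to 5% range is small against both the confidence interval and the detectable HR of 1.69. It is still an avoidable bias in the primary estimate, and the three wordings should be reconciled.

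**What to change.** In Section 4.1, the note to Figure 1 and Section 4.2.2.2 (and Appendix A if it differs), use one rule:

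1. Define non-exposed by the last Cervarix dose on or before the first day of gestation, given 120 days to 18 months earlier.
2. State that any dose placing LMP in the −30 to +90 day window makes the woman exposed and not non-exposed. Without this, a woman dosed within 30 days after LMP would meet both definitions.
3. Ignore doses given after the outcome.
4. If a dose is given during pregnancy more than 30 days after LMP, keep the woman and censor at that dose. Add this to the censoring lists in Sections 5.2.5.3, 5.5.3.1 and 5.6.3.1. It assumes that receiving the dose is unrelated to the later risk of loss.
5. Report how many women are affected, by outcome, and run the present Section 4.1 rule as a sensitivity analysis.

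The cost is a few lines of text and one extra model run on dates the study already needs. The downside is slightly shorter follow-up for a few women.

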4.2. Cohorts identification and follow-up

Cohort identification will be done in a stepwise approach using defined algorithms (see Appendix A).

4.2.1. Screened population

The screened population will be comprised of all women that have been vaccinated with HPV vaccine. Medical codes for HPV vaccination are: 93489 (first dose), 93621 (second dose), 95554 (third dose).

4.2.2. Eligible population

The eligible population will be comprised of all subjects included in CPRD *GOLD* who fulfil to the inclusion/exclusion criteria.

(Amended 14 March 2013)

4.2.2.1. Inclusion criteria for exposed cohort

All subjects must satisfy all of the following criteria at entry into the exposed cohort:

- Full date (day/month/year) of first day of LMP available in the database or calculated from Estimated date of delivery (EDD) (day/month/year)
- Female, aged between, and including, 15 and 25 years of age at LMP
- Recorded in the CPRD *GOLD* for at least 12 months at LMP

- First day of LMP available in the database or calculated from EDD (day/month/year) between September 1st 2008 and June 30th 2011
- At least one dose of *Cervarix* received between September 1st, 2008 and June 30th, 2011
- Full date (day/month/year) of *Cervarix* vaccination(s) available
- First day of LMP available in the database or calculated from EDD between 30 days before and 90 days after any dose of *Cervarix*
- Subject defined as acceptable in CPRD **GOLD**¹

(Amended 14 March 2013)

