4.2.2.3. Exclusion criterion for exposed cohort

The following criterion should be checked at the time of entry into the exposed cohort. If this exclusion criterion applies, the subject must not be included in this cohort:

- Female with the first day of LMP between 30 days before and 90 days after at least one dose of unspecified HPV vaccine and/or *Gardasil*.

¹ Defined in Appendix A. CPRD **GOLD** indicates whether the patient has met certain quality standards (based on an 'internal CPRD **GOLD** check') **(Amended 14 March 2013)**

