5.2.5.2. First day of gestation

Definition of first day of gestation will be as follows:

1. the day reported as the first day of her LMP,
2. the day adjusted based on available ultrasound scan test data performed at week 12 (± 2 weeks) after first day of LMP. The first day of gestation will be adjusted only if there is a discrepancy between the first day of LMP and the ultrasound-based first day of gestation of seven days or more. Associated free text will be reviewed for the ultrasound scan test performed to adjust for the first day of gestation when needed,
3. if ultrasound scan test data is not available at week 12 (± 2 weeks) after first day of LMP, other ultrasound scan tests will be used to adjust for the first day of gestation knowing that accuracy of gestational age estimation via ultrasound decreases over time as shown in Table 6.

Table 6 Adjustment of the first day of gestation using ultrasound scan test

Ultra-sound completed (Wk)	Ultrasound accuracy (days)	Subject-reported first day of gestation will be adjusted if discrepancy is greater than:
]0-14]	5 - 7	7 days compared to ultrasound-based LMP date
]14-26]	10 - 14	14 days compared to ultrasound-based LMP date
≥ 27	21	21 days compared to ultrasound-based LMP date

All studied pregnancies will be confirmed by the occurrence of at least one other pregnancy identifier between the first day of gestation and the date of end of pregnancy. List of codes (read codes) of pregnancy identifiers are detailed in Appendix A.

Based on the defined first day of gestation, the exposed status (exposed vs. non-exposed) could be adjusted and the subjects will be reassigned to the correct cohort.

5.2.5.3. Time from first day of gestation to spontaneous abortion (UK and US definition)

The primary and first secondary endpoints are the occurrence of spontaneous abortion during the first 23 weeks of gestation (UK definition) and during the first 19 weeks of gestation (US definition). The time (day) from first day of gestation to spontaneous abortion will be computed as the difference between the date of spontaneous abortion and the date of first day of gestation + 1 day.

Time from first day of gestation to spontaneous abortion will be censored at the first of the following events:

- At the end of week 23 (or week 19) for women still pregnant at the beginning of week 24 (or week 20)
- At the time of induced or therapeutic abortion

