5.2.5.4. Other derived variables

The following variables will be derived from the CPRD *GOLD* data:

- Woman's date of birth will be defined as the 15th of the birth month and birth year. If the birth month is missing, the birth date will be defined as the 30th June of the birth year
- Incomplete dates will be substituted as follows for calculation of age and/or time to event; if the day is missing the date will be defined as the 15th of the month, if both the day and the month are missing, the date will be defined as 30th June of the year
- Age at first day of gestation will be computed as the difference between the first day of gestation and the date of birth and will be presented in completed year

- Age at a specific event will be computed similarly
- The time from first day of gestation to a specific event (e.g. spontaneous abortion) will be computed as the difference between the date of event (Date1) and the date of first day of gestation (Date0) + 1 and it will be represented in days.

(Amended 14 March 2013)

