5.6.3. Statistical models

5.6.3.1. Cox proportional hazards model

Cox model will be computed using the SAS PHREG procedure. The dependent variable is the time between first day of gestation and the event or at censoring.

For the spontaneous abortion analysis, time to event for subject with no spontaneous abortion will be censored at the earliest of the following time-points:

- 161 days (end of week 23) or 133 days (end of week 19)
- Lost-to-follow up (*de*-enrolment from CPRD *GOLD*) (**Amended 14 March 2013**)
- Mother's death
- Pregnancy termination

The main model (Model 1) will include the exposure status (exposed vs. non-exposed) as a binary independent variable and the age at first day of gestation as a continuous covariate. The adjusted HR will be derived as the exponential of the coefficient associated with the exposure status and its 95% Wald CI.

Survival curve will be depicted for the exposed and non-exposed cohort (using the Option Plots(overlay)=survival in the SAS PHREG procedure).

The following models will also be computed as sensitivity analyses:

Model 2: A Cox model including, in addition to the age at first day of gestation, other covariates

- Smoking during pregnancy (3 classes: yes, no, unknown)
- Exposure to H1N1 pandemic (yes, no)
- Region (class variable)
- Alcohol consumption during pregnancy (3 classes: yes, no, unknown)
- Diabetes during pregnancy (3 classes: yes, no, unknown)

- High blood pressure during pregnancy (3 classes: yes, no, unknown)
- Number of previous pregnancies (sum of the number of previous births and the number of previous abortions)
- Vaccination with another vaccine within 90 days before first day of gestation or within the 90 days after first day of gestation (binary variable)
- Use of contra-indicated drugs during the first trimester of pregnancy (three classes: non contraindicated drug, manufacturer advice “to-use with caution” drugs, manufacturer mentioned advice “to-avoid” drugs)

Covariates occurring in less than 5% of the subjects (percentage will be computed over both exposed and non-exposed cohorts) will not be included in the model.

Model 3: A Cox model will compare the exposed cohort according to the number of *Cervarix* doses (3 classes: 1 dose, 2 doses, 3 doses) vs. the non-exposed cohort, using the same model as for the primary analysis (model 1). In this model, the exposed women with more than 3 doses of *Cervarix* will not be included.

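### The exposed-cohort definition does not require the qualifying dose to precede the pregnancy outcome, so a loss dated before the dose counts as a vaccine-exposed event

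*Combined protocol and SAP*

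**What the plan says.** Section 4.1 defines the primary exposed cohort as "women with the first day of LMP: between 30 days before and 45 days after any" dose of the study vaccine. Section 4.2.2.1 sets the wider eligibility window: "First day of LMP available in the database or calculated from EDD between 30 days before and 90 days after any dose of" the vaccine. Both are rules about the distance between LMP and a dose. Neither mentions the outcome.

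The non-exposed definition in section 4.1 does: it requires no further "dose before the outcome".

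The only exclusion for the exposed cohort (section 4.2.2.3) concerns "at least one dose of unspecified HPV vaccine and/or" the other HPV vaccine.

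Section 5.2.5.2 adds a confirmation rule: "All studied pregnancies will be confirmed by the occurrence of at least one other pregnancy identifier between the first day of gestation and the date" on which the pregnancy ended. That identifier need not fall at or after the dose. The ultrasound step in the same section can move a woman between cohorts, but only by re-dating gestation.

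For the analysis, section 5.6.3.1 states "The dependent variable is the time between first day of gestation and the event or at censoring", and "The main model (Model 1) will include the exposure status (exposed vs. non-exposed) as a binary independent variable". Exposure is therefore fixed from the first day of gestation. None of Models 1 to 4 has delayed entry or time-varying exposure.

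**The concern.** A loss that happened before the dose cannot have been caused by it. Under the written rules, a pregnancy lost 24 days after LMP in a woman whose only qualifying dose came 28 days after LMP is an exposed spontaneous abortion, in a study whose purpose is to assess losses around vaccination.

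The bias depends on how loss and dosing are related:
- If dosing is unrelated to whether the pregnancy has been lost, the pre-dose events and pre-dose time offset each other when the true HR is 1, and a real effect is slightly diluted.
- If an early loss makes a dose more likely, the HR is pushed up. This is plausible because section 1.2 says the vaccine is not recommended during pregnancy.
- If an early loss makes a dose less likely, pre-dose days become partly event-free exposed time and the HR is pushed down.

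The wording can also place one pregnancy in both cohorts. Take LMP 125 days after dose 2, a loss 20 days later, and dose 3 five days after that. LMP is 25 days before dose 3, so she is exposed. Counting doses up to the outcome, dose 2 is her last and LMP is 125 days after it, so she is also non-exposed. The note to Figure 1, which lets an earlier dose be the last only if none followed, points the other way.

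**Working it through.** **The plan's own figure.** Section 5.4 states 98% power at HR 2.0 for the primary window. Freedman's log-rank formula with 243 exposed and 667 non-exposed (section 3.2), an 11.5% event rate and two-sided 5% (section 5.4) gives:
- Events = 243 × (1 − 0.885²) + 667 × 0.115 = 52.7 + 76.7 = 129.4.
- Allocation ratio φ = 243/667 = 0.364.
- z = √(129.4 × 0.364)/(1 + 2 × 0.364) − 1.96 = 2.01, so power is 97.8%.

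This reproduces the stated figure when the 20% dropout is not applied. The point here does not rest on it.

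**Inputs for the size.** From the documents: 243 exposed, 11.5% risk, follow-up to day 161 (section 5.6.3.1), pregnancy onset at LMP+14 (Glossary). Assumptions, because the documents give neither dose timing relative to LMP nor the timing of losses: LMP uniform over the window, one qualifying dose per woman, constant hazard.

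**Women dosed on or after LMP.** The primary window has 30 + 45 + 1 = 76 days, of which 31 place the dose 0 to 30 days after LMP. 243 × 31/76 = 99 women (41%).

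**Expected exposed losses.** 243 × 0.115 = 27.9. Cumulative hazard = −ln(0.885) = 0.122.

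**Losses expected before the dose.**

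| Hazard starts at | Pre-dose woman-days at risk | Daily hazard | Pre-dose losses | Range if 20% to 60% are dosed after LMP |
|---|---|---|---|---|
| LMP | 243/76 × (0+1+…+30 = 465) = 1,487 | 0.122/161 | 1.1 | 0.55 to 1.65 |
| LMP+14 | 243/76 × (1+2+…+16 = 136) = 435 | 0.122/147 | 0.36 | 0.18 to 0.53 |

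These are 4.0% and 1.3% of the 27.9 expected exposed losses. The −30/+90 window gives similar counts: 379/121 × 465 × 0.122/161 = 1.1, or 379/121 × 136 × 0.122/147 = 0.35, of 379 × 0.115 = 43.6.

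**Repeat doses.** The trial report cited in section 9 used a 0, 1, 6 month schedule. Assuming that schedule here, with doses at days 0, 30 and 180, LMP qualifies on days −30 to 75 (106 days) and 150 to 225 (76 days), 182 in all. The first qualifying dose falls on or after LMP on 31 + 31 = 62 of these, or 34% rather than 41%.

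**If early loss prompts a dose.** Adding k extra entrants, each with a loss, to a cohort with true HR 1.0 gives HR ≈ ln(1 − (27.9+k)/(243+k)) / ln(0.885): 1.03 for k = 1, 1.10 for k = 3, 1.17 for k = 5.

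**If only the ordering rule were added.** Dropping 0.36 to 1.1 losses while still counting time from the first day of gestation multiplies the crude ratio by about 0.99 to 0.96. That is the guaranteed event-free time that delayed entry removes.

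**Power after the fix.** At HR 2.0, with hazard from LMP, about 2.2 exposed losses precede the dose. 129.4 − 2.2 = 127.2 events gives 97.6%.

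**The case against.** Several points on the other side stand.

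- A loss within 30 days of LMP must occur within about 16 days of pregnancy onset as the Glossary defines it, and section 5.2.5.2 requires a second pregnancy identifier before the end of pregnancy. Few such losses will be confirmed, so even 0.36 may be high.
- A Cox model uses risk sets only at event times. Every woman dosed after LMP has entered by 30 days after it. If neither cohort has a loss by then, delayed entry leaves the HR exactly unchanged.
- Appendix A holds the extraction algorithms and is not in the text reviewed. A rule there cannot be excluded. If one exists, sections 4.1 and 4.2.2.1 should state it.
- Section 5.6.2 lists each outcome with exposure status and gestational age, so early exposed losses can be found. The listing as described does not include the dose date, and it does not change the model.
- The FDA requested the −30/+45 window. That fixes the window, not the order of dose and loss within it.

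A reader might infer more than the documents support. The 41% dosed on or after LMP is not a misclassification rate: only losses before the dose are misclassified, and earlier qualifying doses lower the share. The pre-dose share of exposed person-time, 0.41 × 15/161 = 3.8%, does not measure bias in a Cox HR. A forecast of one or two pre-dose events in the primary window is at or above the upper end of the calculation.

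**Conclusion.** The gap is real in the text: a stated rule counts a loss before the woman's only qualifying dose as an exposed primary event, and no section supplied corrects it. The expected size is small, about 0.4 to 1 of roughly 28 exposed events in the primary window, with almost no effect on power (97.8% to 97.6% under the less favourable assumption). This rests on LMP uniform over the window and a constant hazard from LMP+14 or from LMP. It would be larger only if early loss makes vaccination more likely, which the documents neither show nor rule out.

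A reader might conclude that the primary HR is biased upward. The documents do not support that: the direction depends on how loss affects dosing, which they do not describe.

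Date handling adds some uncertainty. LMP and vaccination dates must be complete, but no such criterion covers the outcome date, and section 5.2.5.4 says "if the day is missing the date will be defined as the 15th of the month". The recorded order of loss and dose may therefore be an artefact.

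**What to change.** 1. State in sections 4.1 and 4.2.2.1 that the qualifying dose must be on or before the date of pregnancy outcome.
2. Remove from the exposed cohort any pregnancy whose only qualifying dose followed the outcome. Place it in the non-exposed cohort only if it meets that cohort's criteria counting doses up to the outcome; most will meet neither definition. Report the number, and flag those whose outcome day was imputed.
3. In the Cox models, use delayed entry for women whose first qualifying dose follows the first day of gestation. Because the plan computes time as a date difference plus one, setting entry to the plain difference between dose date and first day of gestation keeps a loss on the dose date in the analysis. This step prevents step 1 from creating guaranteed event-free exposed time, and alters the HR only if losses occur by about day 30.

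The exposure window stays as it is. The cost is two protocol sentences, one entry-time variable in the existing PHREG code, and possibly a very few events leaving the exposed cohort. No new data are needed.
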